## 4.4 Analysis Populations

The following analysis populations will be defined.

- Intent-to-Treat (ITT) Population: The Intent-to-Treat (ITT) population will be defined as all subjects who meet the enrollment criteria and are enrolled in the study.
- Safety Population: The Safety population will be defined as all subjects who receive any amount of IP.
- Per Protocol (PP) Population: The PP population will include subjects who have no protocol deviations/violations that could significantly impact the completeness, accuracy and/or reliability of the trial data. The list of subjects in the per protocol population will be compiled prior to database lock.

A summary of the number and percentage of subjects in each analysis population will be provided. A listing of subject assignment into each analysis population will also be displayed.

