## 8.3. Screen Failures

Any subject who provides written informed consent/assent and is ultimately not infused for whatever reason will be classified as a screen failure. All subjects, including screen failures, must be accounted for in the clinical database.

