#### 13.2.4. Reporting Adverse Events

All adverse events are collected from the time of signing informed consent for trial participation until completion of 6 months or early termination, whichever occurs first. All AEs occurring after the initiation of the IV catheter placement for the initial dose of CAP-1002 will be considered treatment emergent. Any ongoing adverse event that has not been resolved at the time of trial completion or early termination for a subject will be marked as ongoing on the adverse event case report form (CRF).

All AEs will be entered into the electronic data capture (EDC) system by trained site personnel at the investigative site.

Expected and unexpected SAEs must be reported to Capricor and entered into the EDC system within 24 hours of discovery of the event. For events that do not have complete information available at the time of initial report, the investigative site will submit all available information at the time of the submission. All SAE Report Forms must be signed by an Investigator and submitted with available source documentation. All source documentation must be de-identified prior to submission.

ALL SAES and subsequent follow-up information must be reported to Capricor, or designee, via email or fax as outlined in the Manual of Procedures and Safety Plan.

All SAEs must be reported to the respective IRB in accordance with the investigative site's policies. Copies of the submission will be collected by Capricor.

All SAEs will be reported to the DSMB at least semi-annually, or more frequently at the discretion of the Medical Monitor.

Capricor will promptly upon discovery, report serious and unexpected adverse events for which there is a reasonable possibility that the investigative therapy (i.e. administration product and/or investigative product) caused the events, to the Food and Drug Administration (FDA) in accordance with 21 CFR 312.32 regulations and ICG E2A guidelines.

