# 2.2 Study Endpoints

#### 2.2.1 Primary Safety Endpoint

The *primary safety endpoints* include the incidence of the following from baseline through the 6-month timepoint:

- Acute respiratory decompensation within 2 hours following Investigational Product (IP) administration
- Hypersensitivity reaction
  - Hypersensitivity reaction is defined as a clinical syndrome including, but not limited to, fever, leukocytosis, or rash with onset  $\leq 2$  hours post infusion and lasting < 24 hours, in the absence of clinical signs of concomitant infection.
- All-cause mortality
- Serious adverse events (SAEs)
- Treatment-emergent adverse events (TEAEs) related to IP or administration procedure
- Immune sensitization syndrome
  - Immune sensitization syndrome shall be defined as:

(a) clinical signs and symptoms consistent with systemic inflammation (e.g., fever, leukocytosis, rash, or arthralgia) with onset  $\geq 24$  hours post infusion and the absence of clinical signs of concomitant infection,

AND

(b) elevation of anti-human leukocyte antigen (HLA) antibodies against the donor cells (i.e., DSAs), detected  $\leq$  30 days following onset of syndrome, of

- (i)  $\geq$  2000 mean fluorescent intensity (MFI) if baseline MFI  $\leq$  1000, or
- (ii)  $\geq$  2 times baseline otherwise

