## 4.1 Treatment Group

The treatment group to be presented will be composed of those subjects who receive CAP-1002.

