# 7 SAFETY ANALYSES

Listings and summaries of the safety parameters will be done for the Safety population. An overall summary table will be presented that summarizes the primary safety endpoints. Safety parameters are described below.

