# 7.1 Adverse Events

Adverse events will be coded using the Medical Dictionary for Regulatory Activities (MedDRA) coding system (Version 21.0). Potential primary safety endpoints, described in Section 2.2.1, will be adjudicated by an independent Clinical Events Committee (CEC).

The following AEs are defined as treatment-emergent AEs (TEAEs):

- AEs occurring after the initiation of the IV catheter placement for the initial dose of IP; or
- AEs with a completely missing start date, or similarly, AEs that started the same month and year as IP administration but with missing start day.

Subject listings of all adverse events as reported will be provided. A separate listing will be done for TEAEs as adjudicated by the CEC. All summary tables will be reported using as adjudicated by the CEC.

An overall summary table will be presented by treatment group that summarizes subject with the following:

- Any TEAEs
- TEAEs by maximum severity
- TEAEs and serious TEAEs by greatest degree of relationship to IP or IP administration
- TEAEs and serious TEAEs by greatest degree of relationship to IP only
- TEAEs and serious TEAEs by greatest degree of relationship to IP administration only
- Serious TEAEs
- TEAEs leading to study discontinuation, and
- TEAEs leading to death

In addition, TEAEs will be summarized overall by system organ class and preferred term and by severity and by relationship to the IP and IP administration procedure.

Deaths, AEs that resulted in study discontinuation, serious adverse events (SAEs), serious TEAEs and AEs within 24 hours of IP administration will be listed and summarized.

Summaries of 'related' TEAEs, will include TEAEs with a reported relationship to IP and/or IP administration of "Probable" or "Possible". Adverse events will be displayed by MedDRA System Organ Class and Preferred Terms, with subjects who have the same adverse event counted only once for that event and with subjects who have more than one adverse event within a System Organ Class counted only once in that System Organ Class. The numbers and percentages of subjects reporting an event as well as the number of events that were reported will be displayed.

Frequency tables will be ordered by decreasing percentage in the SOCs, then alphabetically. Within each SOC, PTs will be ordered by decreasing percentage then alphabetically.

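### Treatment emergence starts at first-dose catheter placement but the SAP Safety population starts at receipt of IP, so a procedure-related event in an attempted but never-infused subject drops out of the primary safety table

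*SAP*

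**What the plan says.** **When an event becomes treatment-emergent.** Protocol 13.2.4: "All AEs occurring after the initiation of the IV catheter placement for the initial dose of CAP-1002 will be considered treatment emergent". SAP 7.1 uses the same trigger: "AEs occurring after the initiation of the IV catheter placement for the initial dose of IP". Neither requires that cells were given.

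**What the endpoint counts.** SAP 2.2.1 lists among the primary safety endpoints: "Treatment-emergent adverse events (TEAEs) related to IP or administration procedure". Protocol 7.2.1 has the same component.

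**Who is summarized under the SAP.** SAP 4.4: "The Safety population will be defined as all subjects who receive any amount of IP". SAP 7: "Listings and summaries of the safety parameters will be done for the Safety population", and in the same paragraph, "An overall summary table will be presented that summarizes the primary safety endpoints". SAP 4.1 adds: "The treatment group to be presented will be composed of those subjects who receive CAP-1002".

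**What the protocol says about the same subject.** Protocol 14.3 makes the Safety population identical to ITT, that is, eligible and enrolled subjects. Protocol 7.1 places enrollment at the signing of consent. Protocol 8.3, however, says: "Any subject who provides written informed consent/assent and is ultimately not infused for whatever reason will be classified as a screen failure".

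**The concern.** The endpoint has two parts, one for the product and one for the procedure that delivers it. The event rule allows for the second part by starting the clock at the catheter. The SAP's population rule does not: it admits a subject only once some product has gone in. A subject can therefore have an event that meets the endpoint definition while being outside the population in which the endpoint is tabulated.

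The situation is possible on the protocol's own account. Section 13.2.1.3 names infection, bleeding, pain, and bruising or hematoma at the access site as risks of the infusion procedure, and none of these needs cells to have been given.

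At stake is the completeness of one row of the primary safety table in a trial of at most 10 subjects, where a single subject is 10 percentage points. It also matters that two analysts, one following the protocol and one the SAP, could report different denominators.

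**Working it through.** The plan has no power, alpha or event-rate figure to reproduce here. Ten is a ceiling without a derivation (Protocol 14.2), and Protocol 14.1 states that there are no formal hypotheses. The check is a trace through the definitions, followed by a sizing.

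**Trace.** Take an eligible subject in whom catheter placement for dose 1 is begun, who has a procedure-related AE, and who never receives IP.

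1. Treatment-emergent? Yes (Protocol 13.2.4, SAP 7.1).
2. Meets the endpoint component? Yes (SAP 2.2.1).
3. In the SAP Safety population? No (SAP 4.4).
4. In the SAP primary safety table? No (SAP 7, with SAP 4.1).
5. In the protocol Safety population? Yes on the wording of 14.3 with 7.1, but 8.3 labels him a screen failure, and the protocol does not say how the two rules combine.
6. Does he have a study day and a baseline? No. SAP 4.2 ties both to the first IP administration, while the endpoint runs from baseline.

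**Cases that are not lost.** A partial or aborted first infusion counts, because some IP was received. A failed access at Month 3 counts, because the subject was exposed on Day 1. A subject whose first attempt fails but who is infused later also counts, and his catheter event is still treatment-emergent.

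**Size if it happens.** Assume 10 subjects reach catheter placement, *k* of them have the traced event, and there are no other related TEAEs. The SAP result is 0/(10 − *k*); counting from catheter placement gives *k*/10. Exact (Clopper-Pearson) 95% limits:

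- *k* = 1: 0/9 = 0% (0 to 33.6%) against 1/10 = 10% (0.25 to 44.5%).
- *k* = 2: 0/8 = 0% (0 to 36.9%) against 2/10 = 20% (2.5 to 55.6%).

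The intervals only show scale. The plan reports AEs as counts and percentages and does not promise intervals for them.

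**How likely.** The documents give no rate of failed first access. If it is *p* per subject (assumption), the chance of at least one among 10 is 1 − (1 − *p*)^10:

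- *p* = 1%: 9.6%
- *p* = 2%: 18.3%
- *p* = 5%: 40.1%
- *p* = 10%: 65.1%

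These are chances of a failed access, not of a lost event. A loss also needs a procedure-related AE and permanent non-infusion. Purely as illustration, if both followed one failed access in ten (assumption), then *p* of 2% to 5% becomes 0.2% to 0.5% per subject. The chance among 10 is then 1 − 0.998^10 = 2.0% to 1 − 0.995^10 = 4.9%.

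**The case against.** The strongest reply is that a safety set of dosed subjects is a defensible choice and that this is a rare edge case in a descriptive trial. Venous access is screened by inclusion criterion 3, and with at most 10 subjects one such case would be noticed. That argument stands as to severity. It does not remove the mismatch between the event rule and the population rule.

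A reader might infer more than the documents support:

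- *That such an event can never enter the endpoint.* This is true of the SAP only. Protocol 14.3 would include an eligible subject of this kind.
- *That the event disappears from the record.* It does not. AEs are collected from consent (Protocol 13.2.4), all potential primary safety endpoints go to the Clinical Events Committee (SAP 7.1.1), SAP 4 promises listings for all subjects, and SAP 5.14 lists screen failures with the reason for non-infusion. SAP 7 does confine safety listings to the Safety population, so listing is probable, not certain. The loss is from the summary table.
- *That the chance of a lost event is 18% to 40%.* That range is the chance of at least one failed first access at an assumed 2% to 5%. The chance of a lost event is lower.
- *That the clock was set at the catheter in order to capture failed attempts, or that failed attempts are the likeliest to carry a procedure AE.* The documents say neither. The same clock also captures catheter events in subjects who go on to be infused.

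It is also fair to object that changing the denominator alone would leave the protocol–SAP conflict, the treatment-group limit and the missing reference day in place. That stands, and the fix has to cover them.

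**Conclusion.** The point holds in limited form. Followed exactly, the SAP leaves a qualifying procedure-related TEAE out of the primary safety table when first administration was attempted and the subject was never infused. The protocol's own Safety definition points the other way, and its screen-failure rule clouds the answer further.

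The effect is at most a few subjects. One among 10, with no other related TEAE, changes the row from 1/10 to 0/9. Its probability cannot be estimated from the documents, and the case is judged uncommon. No hypothesis test depends on it. This is a minor definitional fault that is worth correcting because correction is cheap.

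**What to change.** 1. Reconcile the Safety population in Protocol 14.3 (and the synopsis) with SAP 4.4, so that one definition governs before database lock.
2. In SAP 4.4, for the single endpoint of TEAEs related to the product or its administration, take as denominator every subject in whom catheter placement for the first dose was begun. Print the number exposed to IP beside it.
3. For this table, except those subjects from the screen-failure class in Protocol 8.3 and from the treatment-group limit in SAP 4.1.
4. In SAP 4.2, use the date of attempted administration as the reference day for a subject who is never infused, and take baseline relative to it.

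The cost is a few sentences across the two documents, with no change to treatment, visits or data collection. The downside is that this row's denominator may contain a subject without cell exposure and may differ from the other rows; the adjacent IP-exposed count makes that visible.

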# 5 STUDY POPULATION PARAMETERS

The study population parameters to be listed and summarized are described below. The ITT population will be used for the listings and summaries. Some of the summaries may also be done for other analysis populations defined in Section 4.4.

## 5.1 Eligibility and Informed Consent

Eligibility and informed consent parameters will be provided in a listing, which will include the following: date of informed consent/assent, participation in HOPE-Duchenne protocol, protocol version, inclusion and/or exclusion criteria that were not met, if applicable, and subject infused with IP and reason subject was not infused, if applicable.

The number of subjects meeting all screening eligibility criteria and reasons for screen failure will be summarized.

## 5.2 Missed Visits and Assessments

A listing of missed efficacy visits and assessments will include visit and/or assessment missed.

## **5.3 Protocol Deviations**

Protocol deviations will be listed and may include, but are not limited to:

- Visit not done or out-of-window
- Assessment not completed or out-of-window
- Inclusion/Exclusion
- Informed Consent/Assent
- IP Administration

The number and percentage of subjects with a protocol deviation will be summarized by protocol deviation category.

## 5.4 Demographics and Baseline Characteristics

Demographic and baseline characteristics will be listed and summarized. Demographic characteristics consist of age, sex, ethnicity, and race. A subject's age in years is calculated using the date of the informed consent/assent and date of birth using the following formula:

Age = [(Informed Consent/Assent Date – Birth Date + 1)/365.25].

Baseline characteristics to be summarized include ulna length, height, weight, and body mass index (BMI). In addition, subjects using wheelchair or scooter for part-time and for full-time will be summarized. For ambulatory subjects, the number of subjects able to perform the 6-Minute Walk Test and total distance walked at baseline will be summarized. Subject's height is either measured (i.e., standing height) or calculated from the subject's ulna length.

#### 5.5 Medical Status Questionnaire

Subjects medical status will be displayed in subject listings, which will include date of completion, frequency of walker and manual/power wheelchair or scooter use, age permanently transitioned to a wheelchair full time, ventilatory support, supplemental O2 use, and frequency of falls.

#### 5.6 General Medical History

General medical history will be coded using MedDRA version 21.0. Medical history will be listed and summarized. The summary will be presented by MedDRA System Organ Class (SOC) and Preferred Term (PT). At each level of subject summarization, a subject will be counted only once if that subject experienced the event more than once.

## 5.7 DMD Medical History

The following DMD medical history will be listed and summarized:

- Age at diagnosis (years),
- Age at first chronic glucocorticoid (years),
- Loss of stair climb and age at loss of stair climb (years),
- Loss of stair descend and age at loss of stair descend (years),
- Use of a walker and age at first walker use (years),

- Part-time use of a manual/power wheelchair or scooter and age at first part-time use of a manual/power wheelchair or scooter (years),
- Transition to full-time use of a manual/power wheelchair or scooter and age at first full-time use of a manual/power wheelchair or scooter (years),
- Start of non-invasive ventilatory support and age non-invasive ventilatory support started (years),
- Use of a medical cough assist device and age at first mechanical cough assist device use (years),
- History of spine surgery,
- History of symptomatic heart failure and age at first symptoms of heart failure (years), and
- History of medical (non-surgical) hospitalizations.

# 5.8 Donor-Specific Antibodies

Donor, donor profiles, allele, HLA, HLA Class, and MFI will be listed by subject and visit. Subject HLA profiles will be provided in a separate listing.

DSA data will be analyzed in the context of immune sensitization syndrome should there be an occurrence.

# 5.9 Physical Examination

Physical examination results will be listed and summarized. Observed status (e.g., normal, abnormal, not done) and changes from baseline in body system-specific physical examination findings will be summarized by visit and at end-of-study (EOS) within each body system.

# 5.10 Prior and Concomitant Medications

Prescription, over-the-counter, and alternative medication use will be coded to drug class, preferred drug name, and generic/trade drug name using the World Health Organization Drug Global dictionary (WHODrug Global) version September 1, 2017. Medications that were stopped before the start of the IP administration procedure will be considered "pre-treatment." All other medications will be considered "concomitant." Medications that were started or ongoing at the time the IP administration procedure was started will be considered "baseline" (a subset of "concomitant"). All reported medications will be listed.

Frequencies and percentages of subjects reporting or receiving each medication will be summarized by WHODrug Global Anatomic Therapeutic Chemical (ATC) Level 2 and Preferred Term. Pre-treatment and baseline medications will be summarized separately.

At each level of subject summarization, subjects who reported one or more medications within that level are only counted once for that level.

# 5.11 Planned Medical/Surgical Procedures

All reported elective medical and/or surgical procedures (e.g., wisdom tooth extraction) that were not the result of an adverse event will be displayed in subject listings. For each procedure, the type of procedure, indication, and start date/time will be reported.

Any administered medication(s) related to the planned medical/surgical procedure(s) will be captured as a concomitant medication.

## 5.12 IP Administration

The number of subjects that completed IP infusion at each visit will be summarized. For each visit, the number of patients who completed IP syringe administration, reason IP syringe was not completed, duration of IP administration (minutes), and calculated total dose of IP syringe delivered (M cells) will be summarized.

For the total dose of IP syringe delivered, 50mL of IP is equivalent to cells of total dose of IP.

Details of IP administration will be displayed in subject listings.

## **5.13 Subject Study Progress**

A listing of subject study progress will show dates of screening, informed consent, IP administration, study visits, and end-of-study (EOS). The number of subjects who completed each visit will be summarized.

# 5.14 Subject Disposition

All screen failures will be listed along with the primary reason for not receiving IP infusion.

Subject disposition will be summarized by treatment group for the ITT population overall and by site. The number of subjects who received IP, the reason for not receiving IP, the number of subjects who completed the study, the number of subjects who were discontinued from the study, and the primary reason for discontinuation will be summarized.

# 6 **EFFICACY ANALYSES**

Listings and summaries of the efficacy parameters will be done for both the ITT and PP populations, unless indicated otherwise. Efficacy parameters are described below.

# 6.1 PUL Scale

All subjects, regardless of ambulatory status, will complete testing the 1.2 module in the same preferred arm. Observed values and changes from baseline, mid- and distal-levels combined and for each dimension (high-level, shoulder; mid-level, elbow; distal-level, wrist and hand) separately, will be summarized. The 95% confidence intervals (CI) for the mean estimates will also be displayed.

The observed values will be displayed in subject listings.

# 6.2 Pulmonary Function Testing

Pulmonary function tests (PFTs) will measure SVC, FVC, FEV1, PEF, MIP, MEP, PCF, and IFR. Observed best values (absolute and percent predicted, if it applies) and changes from baseline will be summarized. The 95% confidence intervals for the mean estimates will also be displayed.

The observed values (absolute, best value and percent predicted, if it applies) will be displayed in subject listings.

# 6.3 Cardiac MRI

LV structure and function as assessed by cardiac MRI include LV (myocardium) mass, , LV endsystolic volume, LV end-systolic volume index, LV end-diastolic volume, LV end-diastolic volume index, , LV stroke volume, LV ejection fraction, systolic wall thickening (anterior LV, lateral LV, inferior LV, septal LV), regional wall motion [dyssynchrony (CURE)], circumferential strain (global, anterior LV, lateral LV, inferior LV, septal LV), LV wall thickness that includes end-systolic wall thickness average (anterior, lateral, inferior, septal) and end-diastolic wall thickness average (anterior, lateral, inferior, septal).

In additional, the LV mass index  $(g/m^2)$  will be calculated as

LV Mass Index  $(g/m^2) = LV$  Mass (g)/BSA  $(m^2)$ 

where Body Surface Area (BSA) = 0.007184 \* Height (cm)0.725 \* Weight (kg)0.425. Height and weight measurements closest to the MRI scan will be used. The standing height will be used, if provided, otherwise, the height from ulna length will be used.

Observed and changes from baseline will be summarized. The 95% confidence intervals for the mean estimates will also be displayed.

The observed values will be displayed in subject listings.

